### 5.3.2. Dose Adjustment in Group 2: Combination of Enzalutamide and GS-5829

Due to the CYP3A4 interaction of the two study drugs, discontinuing enzalutamide for more than 2 weeks may lead to a clinically significant increase in GS-5829 exposure. Therefore, in the event of any hematologic or non-hematologic toxicity in the combination arm, even if the toxicity is attributed by the investigator only to enzalutamide, both enzalutamide and GS-5829 may need to be interrupted or discontinued according to [Table 5-2](#).

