Enzalutamide is a strong CYP3A4 inducer, which has been demonstrated to decrease the AUC of a CYP3A4 substrate (midazolam) by 86%; therefore further dose escalation of the combination therapy will be performed in these subjects prior to initiation Phase 2 Dose Expansion. As the concern is for decreased GS-5829 exposure, the initial dose level of the combination therapy will be 160 mg of enzalutamide combined with a starting dose of GS-5829 that has been determined to be safe and tolerable in the single agent dose escalation. Enzalutamide dosing will begin approximately 2 weeks prior to GS-5829 dosing to achieve near maximal CYP3A4 induction to reduce changes in GS-5829 exposure over the first cycle. PK evaluations will be performed and if indicated and supported by PK, safety and tolerability, additional cohorts with higher doses and/or more frequent dosing (ie, twice daily) of GS-5829 in combination with enzalutamide may be tested. The total daily dose will not increase by more than 100% in the next cohort.

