**Table 5-2. Dose Reduction in Group 2: Combination of Enzalutamide and GS-5829**

	Considered related to enzalutamide	Considered related to GS-5829	Considered potentially related to both enzalutamide and GS-5829 or unknown relationship
Grade 4 toxicity	Interrupt dosing of enzalutamide for at least 7 days and not longer than 17 days until symptoms improve to $\leq$ Grade 2, then resume at 120 mg. If subject is already at 120 mg, or it takes longer than 17 days to improve $\leq$ Grade 2, then permanently discontinue both enzalutamide and GS-5829.	Permanently discontinue both enzalutamide and GS-5829	Permanently discontinue both enzalutamide and GS-5829
Grade 3 toxicity	Interrupt dosing of enzalutamide for at least 7 days and a maximum of 17 days until symptoms improve to $\leq$ Grade 2, then resume at 120 mg. If subject is already at 120 mg, or it takes longer than 17 days to improve $\leq$ Grade 2, then permanently discontinue both enzalutamide and GS-5829.	Interrupt GS-5289 for a maximum of 28 days until the toxicity resolves to $\leq$ Grade 1 or returns to baseline level. Following resolution of the toxicity or the toxicity returns to baseline level, treatment may be restarted at a reduced dose as per Table 5-1 .  Enzalutamide dosing does not need to be interrupted or dose reduced.	Interrupt both enzalutamide and GS-5829 for at least 7 days and a maximum of 17 days until symptoms improve to $\leq$ Grade 1 or return to baseline level at which time subjects may resume enzalutamide at either 120 mg or 160 mg and resume GS-5829 at a reduced dose per Table 5-1 . If a subject is already at 120 mg of enzalutamide, they must discontinue.

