Intolerable Grade 2 Toxicity	Interrupt dosing a maximum of 17 days until symptoms improve to $\leq$ Grade 2, then resume at either 160 mg or 120 mg. If subject is already at 120 mg, or it takes longer than 17 days to improve $\leq$ to Grade 1 then permanently discontinue.	Interrupt GS-5829 for a maximum of 28 days until the toxicity resolves to $\leq$ Grade 1 or returns to baseline level. Following resolution of the toxicity or the toxicity returns to baseline level, treatment may be restarted at either the same dose or a reduced dose as per Table 5-1 .	Interrupt both enzalutamide and GS-5829 for a maximum of 17 days until symptoms improve to $\leq$ Grade 1 or return to baseline level, at which time subjects may resume enzalutamide at either 120 mg or 160 mg and GS-5829 at the same dose or a reduced dose per Table 5-1 . A subject may not dose reduce enzalutamide to less than 120 mg once daily

If a subject develops a recurrence of the same Grade 3 or 4 hematologic or non-hematologic toxicity that the investigator considers related to GS-5829 and is clinically significant at the lower dose of GS-5829, then the subject should be permanently discontinued from all study drug(s).

Subjects whose dose of enzalutamide is interrupted for a non-drug related toxicity for up to 17 days, or whose dose of GS-5829 is interrupted for up to 28 days and are deemed by the investigator to be clinically benefiting from the combination treatment prior to dose interruption, may resume combination treatment. Non-drug related dose interruptions for longer than 17 days (enzalutamide) or 28 (GS-5829) days in patients who do not have disease progression may be considered for resumption of study drugs after discussion with the Medical Monitor.

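### Table 5-2 lets GS-5829 continue for up to 3 days past the 2-week limit off enzalutamide that Section 5.3.2 itself warns about

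*Protocol*

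**What the plan says.** Protocol Section 5.3.2 opens with the CYP3A4 interaction and states that "discontinuing enzalutamide for more than 2 weeks may lead to a clinically significant increase in GS-5829 exposure". It draws the consequence that, "even if the toxicity is attributed by the investigator only to enzalutamide, both enzalutamide and GS-5829 may need to be interrupted or discontinued", with the detail left to Table 5-2.

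The table's column for toxicity related to enzalutamide reads:

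- **Grade 4:** "Interrupt dosing of enzalutamide for at least 7 days and not longer than 17 days until symptoms improve to" Grade 2 or lower, then resume at 120 mg.
- **Grade 3:** "Interrupt dosing of enzalutamide for at least 7 days and a maximum of 17 days until symptoms improve to" Grade 2 or lower, then resume at 120 mg.
- **Both cells:** if the subject is already at 120 mg, or recovery takes longer than 17 days, "then permanently discontinue both enzalutamide and GS-5829". This is the only action on GS-5829 in either cell.
- **Intolerable Grade 2:** "Interrupt dosing a maximum of 17 days until symptoms improve to" the stated grade. No drug is named.

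Below the table, a paragraph on non-drug-related interruptions covers "Subjects whose dose of enzalutamide is interrupted for a non-drug related toxicity for up to 17 days". It sets conditions for resuming treatment and does not say what happens to GS-5829 in the meantime.

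**The concern.** The section names a time limit and points to the table as the safeguard, but two cells of that table allow the limit to be passed with GS-5829 still being taken.

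This matters because the combination dose of GS-5829 is chosen with the inducer on board. Section 1.3.1 explains that "Enzalutamide dosing will begin approximately 2 weeks prior to GS-5829 dosing to achieve near maximal CYP3A4 induction to reduce changes in GS-5829 exposure". Section 3.2 allows the combination dose to rise above the dose found tolerable as a single agent, depending on the observed interaction and tolerability. If induction fades while such a dose continues, exposure moves towards that of a single-agent dose which may not have been shown to be tolerable.

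The margin may be thin. Section 1.3.1 cites a narrow therapeutic index in dogs. Section 1.5 reports dose-limiting adrenal hemorrhage at 4 mg and Grade 3 thrombocytopenia at 3 mg. The subjects concerned would already have an unresolved Grade 3 or 4 toxicity.

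**Working it through.** The plan states no figure to reproduce. The check sets the warning against the table and takes one difference.

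**Inputs**

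- Warning threshold: more than 2 weeks off enzalutamide, that is, beyond day 14 of a hold (Section 5.3.2).
- Longest enzalutamide hold in the Grade 3 and Grade 4 enzalutamide-related cells: 17 days (Table 5-2).
- GS-5829 schedule: once daily (Section 3.3), with twice-daily combination cohorts possible (Section 1.3.1).

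**Length of the gap**

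- Longest hold - threshold = 17 - 14 = 3 days, namely days 15, 16 and 17.
- Once daily: 3 × 1 = 3 doses.
- Twice daily: 3 × 2 = 6 doses.

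**How often it can occur**

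A subject on 160 mg who is held under one of these cells resumes at 120 mg. A further such event at 120 mg ends both drugs. These two cells therefore allow at most one hold, and at most 3 days of overlap, per subject.

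**Could the text be read as already holding GS-5829?**

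- The Grade 3 cell for toxicity related to both drugs, or of unknown relationship, explicitly interrupts both. The table says so when it means it.
- The Grade 3 cell for toxicity related to GS-5829 says what to do with enzalutamide (no interruption or reduction needed). The enzalutamide cells have no matching instruction for GS-5829.
- Section 5.3.1 requires a GS-5829 hold only for toxicity considered related to GS-5829.
- Section 3.4 permits discontinuation at the investigator's discretion, and Section 7.5 has toxicities brought to the Medical Monitor. Neither requires a hold at day 14.

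No provision closes the gap. The intolerable Grade 2 cell and the non-drug-related paragraph are different: they are unclear about GS-5829 and cannot be said to authorise dosing past day 14.

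**The case against.** The case for leaving the table alone has five parts.

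1. **The 17-day cap looks deliberate.** It recurs throughout Table 5-2, and Section 5.3 gives the enzalutamide lead-in as 14 days with a window of 3 days either way, so 17 could be 2 weeks plus that tolerance. The documents do not say this, and that window governs the start of GS-5829 rather than a hold. Even if it is the origin, the rule still permits dosing past the stated limit.
2. **The warning is soft.** It says exposure may rise, and the table does stop both drugs after 17 days. That is fair, and it bears on the weight of the point. It does not explain why GS-5829 should continue between days 14 and 17.
3. **The risk depends on the dose.** The combination starts at or below the single-agent MTD, or at a single-agent dose already judged safe. At such a dose, losing induction would be expected to return exposure towards levels already tolerated. This stands. The concern applies mainly if the combination dose is escalated beyond the single-agent dose, which is permitted but not required.
4. **The remedy is partial.** Restarting both drugs together does not deal with the time needed to rebuild induction, which Section 1.3.1 puts at about 2 weeks, and enzalutamide restarts at only 120 mg. This also stands. The remedy removes the exposure on days 15 to 17 and no more, although a joint restart is what the table already allows in its cells for toxicity related to both drugs.
5. **Section 5.3.2 and Table 5-2 are headed Group 2, which never opened.** That is so, although the section's text speaks of the combination arm, which may extend it to Phase 1b.

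**Conclusion.** The inconsistency is real. A subject managed in full compliance with the Grade 3 or Grade 4 enzalutamide-related cell can receive GS-5829 for up to 3 days in a period the protocol itself regards as potentially unsafe.

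The consequence is limited. It requires Grade 3 or 4 toxicity attributed to enzalutamide alone, a subject still on 160 mg, and no recovery by day 14. It amounts to at most 3 once-daily doses, once per subject under these cells.

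The conclusion takes the 2-week warning as day 14 of the hold. No fold-change in exposure is claimed, because the documents give none for GS-5829, and no harm is shown. Because the study was discontinued during dose escalation (SAP Section 1), this is a comment on the written plan. The correction is worth making because it is specific, protects subjects and costs little.

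**What to change.** In the Grade 3 and Grade 4 enzalutamide-related cells of Table 5-2, add a sentence such as: GS-5829 must be interrupted no later than day 14 of the enzalutamide hold (last dose on day 14 at the latest) and may restart only when enzalutamide is resumed.

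Apply the same sentence to any enzalutamide-only hold under the intolerable Grade 2 cell and the non-drug-related paragraph, where it would also settle what happens to GS-5829. State that it covers all combination cohorts.

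The cost is one sentence in two cells, repeated in two further places. For subjects, it means up to 3 missed once-daily GS-5829 doses (days 15 to 17) per Grade 3 or 4 hold, in a small number of people.

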**Table 5-2. Dose Reduction in Group 2: Combination of Enzalutamide and GS-5829**

	Considered related to enzalutamide	Considered related to GS-5829	Considered potentially related to both enzalutamide and GS-5829 or unknown relationship
Grade 4 toxicity	Interrupt dosing of enzalutamide for at least 7 days and not longer than 17 days until symptoms improve to $\leq$ Grade 2, then resume at 120 mg. If subject is already at 120 mg, or it takes longer than 17 days to improve $\leq$ Grade 2, then permanently discontinue both enzalutamide and GS-5829.	Permanently discontinue both enzalutamide and GS-5829	Permanently discontinue both enzalutamide and GS-5829
Grade 3 toxicity	Interrupt dosing of enzalutamide for at least 7 days and a maximum of 17 days until symptoms improve to $\leq$ Grade 2, then resume at 120 mg. If subject is already at 120 mg, or it takes longer than 17 days to improve $\leq$ Grade 2, then permanently discontinue both enzalutamide and GS-5829.	Interrupt GS-5289 for a maximum of 28 days until the toxicity resolves to $\leq$ Grade 1 or returns to baseline level. Following resolution of the toxicity or the toxicity returns to baseline level, treatment may be restarted at a reduced dose as per Table 5-1 .  Enzalutamide dosing does not need to be interrupted or dose reduced.	Interrupt both enzalutamide and GS-5829 for at least 7 days and a maximum of 17 days until symptoms improve to $\leq$ Grade 1 or return to baseline level at which time subjects may resume enzalutamide at either 120 mg or 160 mg and resume GS-5829 at a reduced dose per Table 5-1 . If a subject is already at 120 mg of enzalutamide, they must discontinue.
Intolerable Grade 2 Toxicity	Interrupt dosing a maximum of 17 days until symptoms improve to $\leq$ Grade 2, then resume at either 160 mg or 120 mg. If subject is already at 120 mg, or it takes longer than 17 days to improve $\leq$ to Grade 1 then permanently discontinue.	Interrupt GS-5829 for a maximum of 28 days until the toxicity resolves to $\leq$ Grade 1 or returns to baseline level. Following resolution of the toxicity or the toxicity returns to baseline level, treatment may be restarted at either the same dose or a reduced dose as per Table 5-1 .	Interrupt both enzalutamide and GS-5829 for a maximum of 17 days until symptoms improve to $\leq$ Grade 1 or return to baseline level, at which time subjects may resume enzalutamide at either 120 mg or 160 mg and GS-5829 at the same dose or a reduced dose per Table 5-1 . A subject may not dose reduce enzalutamide to less than 120 mg once daily

If a subject develops a recurrence of the same Grade 3 or 4 hematologic or non-hematologic toxicity that the investigator considers related to GS-5829 and is clinically significant at the lower dose of GS-5829, then the subject should be permanently discontinued from all study drug(s).

Subjects whose dose of enzalutamide is interrupted for a non-drug related toxicity for up to 17 days, or whose dose of GS-5829 is interrupted for up to 28 days and are deemed by the investigator to be clinically benefiting from the combination treatment prior to dose interruption, may resume combination treatment. Non-drug related dose interruptions for longer than 17 days (enzalutamide) or 28 (GS-5829) days in patients who do not have disease progression may be considered for resumption of study drugs after discussion with the Medical Monitor.

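### Table 5-2: for an intolerable Grade 2 toxicity attributed to enzalutamide, the grade for resuming (≤ Grade 2) and the grade for avoiding permanent discontinuation (≤ Grade 1) conflict, and the stop clause names no drug

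*Protocol*

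**What the plan says.** Table 5-2 in Protocol Section 5.3.2 has nine cells: three severity rows (Grade 4, Grade 3, intolerable Grade 2) by three attributions (enzalutamide, GS-5829, both or unknown).

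The cell at issue is intolerable Grade 2 attributed to enzalutamide. It reads "Interrupt dosing a maximum of 17 days until symptoms improve to" ≤ Grade 2, "then resume at either 160 mg or 120 mg". It then covers two cases: the subject is already at 120 mg, or more than 17 days are needed to improve "to Grade 1 then permanently discontinue". The sentence ends there, without saying which drug or drugs are stopped.

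Three neighbouring cells are relevant:

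- The enzalutamide-related Grade 3 and Grade 4 cells use ≤ Grade 2 both to resume and to stop, and end "then permanently discontinue both enzalutamide and GS-5829".
- In the same row, the cell for toxicity attributed to both drugs or of unknown cause requires ≤ "Grade 1 or return to baseline level, at which time subjects may resume enzalutamide at either 120 mg or 160 mg".
- Also in the same row, the GS-5829-related cell requires ≤ Grade 1 or baseline before GS-5829 restarts.

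The text introducing the table gives the pharmacological reason for its rules: "discontinuing enzalutamide for more than 2 weeks may lead to a clinically significant increase in GS-5829 exposure". It adds that, even when a toxicity is attributed to enzalutamide alone, "both enzalutamide and GS-5829 may need to be interrupted or discontinued", and refers to Table 5-2 for the detail.

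**The concern.** This is an operative dosing rule, and within one cell it gives two instructions that the same subject can trigger together. The row is entered at Grade 2. If the symptoms ease to a tolerable level but remain Grade 2, the first sentence permits enzalutamide to resume. If they are still Grade 2 after day 17, the second sentence requires permanent discontinuation. A site following the cell literally could restart a subject and then have to withdraw him, and two sites could treat identical subjects differently.

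The missing drug name matters because of the interaction described in Section 5.3.2. A site that stopped enzalutamide only would leave the subject on GS-5829 while CYP3A4 induction is lost. The documents give no figure for the resulting rise in GS-5829 exposure. The only induction figure is the 86% fall in midazolam AUC in Protocol Section 1.3.1, and it is not extrapolated here.

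**Working it through.** No sample size, power or interval is involved, so the check sets the nine cells side by side.

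| Row | Attributed to | Grade to resume | Grade that avoids stopping | Drug named in stop clause |
|---|---|---|---|---|
| Grade 4 | enzalutamide | ≤ 2 | ≤ 2 | both |
| Grade 4 | GS-5829 | none (outright stop) | none | both |
| Grade 4 | both/unknown | none (outright stop) | none | both |
| Grade 3 | enzalutamide | ≤ 2 | ≤ 2 | both |
| Grade 3 | GS-5829 | ≤ 1 or baseline | no stop clause | – |
| Grade 3 | both/unknown | ≤ 1 or baseline | stop if already at 120 mg | none named |
| Intolerable Grade 2 | enzalutamide | ≤ 2 | ≤ 1 | none named |
| Intolerable Grade 2 | GS-5829 | ≤ 1 or baseline | no stop clause | – |
| Intolerable Grade 2 | both/unknown | ≤ 1 or baseline | no stop clause | – |

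**Thresholds.** Three cells state both a resume grade and a stop grade, all in the enzalutamide column. Two agree (≤ 2 and ≤ 2). Only the intolerable Grade 2 cell differs (≤ 2 and ≤ 1).

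**Who is caught.** Take a subject on 160 mg with an intolerable Grade 2 event. On some day d, with d at most 17, the symptoms become tolerable but are still Grade 2.

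- Resume rule: the grade is ≤ 2 and d ≤ 17, so enzalutamide may restart at 160 mg or 120 mg.
- Stop rule: if the grade is still 2 after day 17, reaching ≤ Grade 1 has taken longer than 17 days, so permanent discontinuation is required.

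Both rules apply. A subject who reaches ≤ Grade 1 by day 17 meets no conflict. Nor does a subject already at 120 mg, whom the cell stops without reference to grade.

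**Drug named.** Stop instructions appear in 3 (Grade 4) + 2 (Grade 3) + 1 (intolerable Grade 2) = 6 of 9 cells. Of these, 3 + 1 = 4 name both drugs and 6 − 4 = 2 name none.

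**Whether other text settles it.**

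- Section 5.3.2 says both drugs may need to be stopped, but only as the table directs.
- Section 5.3.1 stops both drugs when a toxicity does not resolve, but in the context of GS-5829-related toxicity.
- Section 3.4 lets the investigator discontinue for toxicity on judgement, and Section 7.5 routes questions to the Medical Monitor. Neither supplies the threshold or the drug.

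**The case against.** The best defence starts from the row label. The trigger is *intolerable* Grade 2, and the cell asks for symptoms to *improve*. A reader might infer from the printed grades that enzalutamide can restart at once, with no improvement at all, because Grade 2 already satisfies ≤ Grade 2. The documents do not support that: the two words together imply at least a move from intolerable to tolerable. This objection stands, and it confines the conflict to tolerable but persisting Grade 2. It does not remove the conflict, because that subject still fails the ≤ Grade 1 limit.

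A second defence confines the stop clause to subjects who are still off drug at day 17. The cell does not say so. On that reading the Grade 1 limit would do no separate work, since anyone at tolerable Grade 2 would already have been allowed to resume.

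On the unnamed drug, the defence is largely right that stopping both is the natural reading, given the rationale in Section 5.3.2. Harm would need a site to choose the less natural reading. A reader might also infer an equal defect in the Grade 3 cell for both or unknown attribution, which ends "If a subject is already at 120 mg of enzalutamide, they must discontinue". That cell opens by interrupting both drugs and nothing in it suggests continuing GS-5829 alone, so naming them there is an optional clarification.

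The consequences are also bounded. Investigators can discontinue for toxicity on their own judgement under Section 3.4, and restarting at 120 mg rather than 160 mg is allowed.

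**Conclusion.** The cell is wrong as written, at minor severity. It contradicts itself for one kind of subject: on 160 mg, with an enzalutamide-attributed intolerable Grade 2 toxicity that becomes tolerable but is still Grade 2 after day 17. Its stop clause should also name the drugs.

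Reach is small. The table is titled for Group 2, and the SAP Introduction states that the study ended without opening Phase 2. The rule can therefore have applied to Phase 1b combination subjects at most, assuming that the reference in Section 5.3.2 to the combination arm includes them. The SAP also states that all Phase 1b subjects have discontinued study drug, so correcting the cell cannot alter anyone's current dosing. Its value lies in the accuracy of this protocol and of any later protocol that reuses the table.

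A reader might infer that the results are affected, or that subjects were over-exposed to GS-5829. Neither follows: no endpoint or analysis depends on this cell, and the documents do not show that any site stopped enzalutamide alone.

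That ≤ Grade 1 and both drugs were intended is an inference from the cell's own stop grade, the rest of its row and the two enzalutamide-related cells above it.

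**What to change.** In the enzalutamide-related intolerable Grade 2 cell of Table 5-2:

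1. State that the drug being interrupted is enzalutamide.
2. Change the grade for resuming from ≤ Grade 2 to ≤ Grade 1, keeping the 17-day maximum and the choice of 160 mg or 120 mg.
3. Keep the stop conditions (already at 120 mg, or more than 17 days to reach ≤ Grade 1), and end the sentence "then permanently discontinue both enzalutamide and GS-5829".

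This keeps the stop grade already printed and brings the resume grade into line with it and with the ≤ Grade 1 standard in the rest of the row. The return-to-baseline alternative in those other cells should not be carried over as a mere edit. No enzalutamide-related cell contains it, and inclusion criterion 5 admits subjects with Grade 2 neurotoxicity, for whom baseline would itself be Grade 2.

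The cost is a wording change in one cell. The small clinical downside is that some subjects at tolerable Grade 2 would resume later. Setting both thresholds at tolerable Grade 2 would also remove the conflict and would resemble the enzalutamide-related cells above, but it would relax the existing stop rule, so the sponsor's clinical team should confirm the choice. Naming both drugs in the Grade 3 cell for both or unknown attribution is optional. Endpoints, sample size and analyses are unchanged.
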